10.1.2.4. Unsolicited adverse events

Unsolicited adverse event summaries are including serious adverse events unless specified otherwise.

Missing severity, relationship with study vaccine, and outcome of unsolicited adverse events will not be replaced and will appear as 'UNKNOWN' when displayed in a statistical output.

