5.4.4. Safety analysis

Primary vaccination and revaccination dose:

The safety analysis will be performed on the ES. A descriptive analysis by group, for the 3 groups pooled up to Month 12, for the RSV_flexible revaccination and RSV_1dose groups pooled vs RSV_annual group for Month 13, Month 18 and Month 24, and by group from Month 25 up to study end, will present a summary of:

- The number and percentage of participants with at least one administration site event (solicited and unsolicited), with at least one systemic event (solicited and unsolicited) and with any AE during the 4-day or 30-day follow-up period will be tabulated with exact 95% CI after each dose. The same computations will be done for Grade 3 AEs, and for Grade 3 non-serious AEs and for AEs resulting in medically attended visit.
- The number and percentage of participants reporting each individual solicited administration site event (any grade, Grade 3 and resulting in medically attended visit) and solicited systemic event (any grade, Grade 3 and resulting in medically attended visit) during the 4-day follow-up period (i.e., on the day of vaccination and 3 subsequent days) will be tabulated for each group after each dose.
- For fever, the number and percentage of participants reporting fever by half degree (°C) cumulative increments during the 4-day follow-up period (i.e., on the day of vaccination and 3 subsequent days) will be tabulated for each group after each dose.
- The incidence of each solicited administration site event and solicited systemic event (any grade and grade 3) will be represented graphically after each dose.

- The number and percentage of participants with any unsolicited AEs during the 30day follow-up period (i.e., on the day of vaccination and 29 subsequent days) with its exact 95% CI will be tabulated for each dose by group and by Medical Dictionary for Regulatory Activities (MedDRA) Primary System Organ Class (SOC), High Level Term (HLT) and preferred term (PT). Similar tabulation will be done for Grade 3 unsolicited AEs, for any causally related unsolicited AEs, for Grade 3 causally related unsolicited AEs and for unsolicited AEs resulting in a medically attended visit. The verbatim reports of unsolicited AEs will be reviewed by a qualified person and the signs and symptoms will be coded according to the MedDRA Dictionary for Adverse Reaction Terminology. Every verbatim term will be matched with the appropriate Preferred Term.

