- The number and percentage of participants with at least one report of SAE classified by the MedDRA Primary SOC, HLT and PTs and reported from Dose 1 up to 6 months post-Dose 1 and from revaccination dose up to 6 months post-revaccination will be tabulated with exact 95% CI. The same tabulation will be presented for causally related SAEs and fatal SAEs,.
- The number and percentage of participants with at least one report of causally related SAEs classified by the MedDRA Primary SOC, HLT and PTs will be reported after each dose and from Day 1 up to study end with exact 95% CI. The same tabulation will be presented for fatal SAEs.
- All SAEs will also be described in detail in a tabular listing.
- All AEs/SAEs leading to study/intervention discontinuation from dose 1 up to study end will be tabulated.
- The number and percentage of participants with at least one report of pIMD classified by the MedDRA Primary SOC, HLT and PTs and reported from Dose 1 up to 6 months post-Dose 1 and from revaccination dose up to 6 months post-revaccination will be tabulated with exact 95% CI. The same tabulation will be presented for causally related pIMDs
- The number and percentage of participants with at least one causally related pIMD classified by the MedDRA Primary SOC, HLT and PTs will be reported after each dose and from Day 1 up to study end with exact 95% CI.
- All pIMDs will also be described in detail in a tabular listing.
- The analyses of unsolicited AEs will include SAEs (unless otherwise specified).

The analysis of safety will also be performed by age category (age at Dose $1: \ge 65$ YOA, ≥ 70 YOA, ≥ 80 YOA, 60-69 YOA and 70-79 YOA) and region (North America, Europe, Asia).

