10.1.2.4. Unsolicited adverse events

Unsolicited AE summaries are including SAEs unless specified otherwise.

Missing severity, relationship with study vaccine, and outcome of unsolicited AEs will not be replaced and will appear as 'UNKNOWN' when displayed in a statistical output.

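### Unsolicited AEs with no recorded relationship or severity stay UNKNOWN, so the causally related and Grade 3 percentages can be understated but never overstated by the rule

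*SAP*

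**What the plan says.** The governing text is SAP Amendment 3, Section 10.1.2.4: "Missing severity, relationship with study vaccine, and outcome of unsolicited AEs will not be replaced". The same sentence adds that such values are shown as UNKNOWN in outputs. Its substance has not changed since the February 2021 SAP, which reads: "Missing severity, relationship with study vaccine, and outcome of unsolicited adverse events will not be replaced". Serious events come under the same heading: "Unsolicited AE summaries are including SAEs unless specified otherwise".

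Section 5.4.4 then plans tables defined by exactly those attributes. For unsolicited AEs: "Similar tabulation will be done for Grade 3 unsolicited AEs, for any causally related unsolicited AEs, for Grade 3 causally related unsolicited AEs". For serious events, a further table is described in these terms: "with at least one report of causally related SAEs classified by the MedDRA Primary SOC, HLT and PTs will be reported after each dose"; it also runs to study end, and pIMDs get a matching table.

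Section 5.1.3 takes all vaccinated participants into these analyses and treats anyone without a reported event as not having had it.

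On collection, the protocol asks the investigator to judge the relationship of each unsolicited AE and SAE (Section 10.3.9.2), to give a causality assessment with the initial report of any SAE or pIMD (Section 8.3.3), and to grade the maximum intensity of every unsolicited AE (Section 10.3.9.1).

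**The concern.** The SAP says what is not done with a missing relationship or severity. It does not say what happens to the event in a table whose numerator depends on that attribute. It does not say whether UNKNOWN gets its own row, and it plans no worst-case or sensitivity table. An event with no relationship cannot be shown as causally related, and one with no severity cannot be shown as Grade 3, while the participant remains in the denominator.

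For a safety summary this is the less cautious direction. Related SAEs and related pIMDs from first vaccination to study end are named secondary endpoints. If their counts turn out to be small, one unassessed event is a sizeable share of the total. The Month 13 and end-of-study analyses are both intended for public posting and a study report (SAP Section 7.1), so a reader of those tables should be able to tell how many events were unassessed.

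**Working it through.** **No plan figure to reproduce.** The documents give no expected rate of missing relationship or severity, and no expected related or Grade 3 rate. The check is therefore a reading of the rules followed by an illustration.

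**Step 1: the rules side by side (SAP Amendment 3).**

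- Denominator: all vaccinated participants (5.1.3).
- Numerators: participants with at least one event recorded as causally related, as Grade 3, or as both (5.4.4).
- Missing attribute: left as UNKNOWN (10.1.2.4).
- By contrast, other missing AE attributes are assigned. A missing administration-site flag becomes systemic (10.1.3.7). An incomplete AE start date in the month or year of a dose, flagged as after vaccination, is set to a dose date (9.1.1).

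Let x be the participants with a known related (or Grade 3) event and u those whose only candidate event is UNKNOWN on that attribute. The tables give x/n. If all u events truly qualified, the rate would be (x + u)/n. The shortfall is therefore between 0 and u/n, and cannot be negative.

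**Step 2: check on group sizes.** Protocol Table 23 uses n = 990 (RSV_annual) and n = 330 (RSV_flexible revaccination). With 1 − (1 − p)^n at p = 0.5%, the probability of at least one event is 99.3% and 80.9%, matching that table.

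**Step 3: value of one participant.** 1/990 = 0.1 percentage points; 1/330 = 0.3 percentage points. For u = 10: 10/990 = 1.0 and 10/330 = 3.0 percentage points.

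**Step 4: illustration with exact (Clopper-Pearson) 95% intervals.** All counts are assumptions. The u = 0 rows show what would be reported if UNKNOWN is left out.

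| n | Known x | UNKNOWN-only u | (x + u)/n | 95% CI |
|---|---|---|---|---|
| 990 | 20 | 0 | 2.0% | 1.2–3.1 |
| 990 | 20 | 1 | 2.1% | 1.3–3.2 |
| 990 | 20 | 2 | 2.2% | 1.4–3.3 |
| 990 | 20 | 5 | 2.5% | 1.6–3.7 |
| 990 | 20 | 10 | 3.0% | 2.1–4.3 |
| 330 | 7 | 0 | 2.1% | 0.9–4.3 |
| 330 | 7 | 1 | 2.4% | 1.1–4.7 |
| 330 | 7 | 2 | 2.7% | 1.3–5.1 |
| 330 | 7 | 5 | 3.6% | 1.9–6.3 |
| 330 | 7 | 10 | 5.2% | 3.0–8.1 |

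**Step 5: rare events.** If 1 to 3 related SAEs are counted (assumed), one further related but unassessed event would add 1/1 = 100% down to 1/3 = 33% to the count. In terms of detection, take a true related rate of 0.5% with a share m of those participants lost to a missing relationship. The probability of seeing at least one is 1 − (1 − 0.005(1 − m))^n:

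| m (assumed) | n = 990 | n = 330 |
|---|---|---|
| 0% | 99.3% | 80.9% |
| 5% | 99.1% | 79.2% |
| 10% | 98.8% | 77.4% |
| 20% | 98.1% | 73.4% |

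With no missing values, nothing in Steps 3 to 5 changes any result.

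**The case against.** The strongest reply is that the protocol deals with this at collection. Causality must accompany the first SAE or pIMD report, must be recorded before the expedited report is submitted, and must be confirmed as reviewed within 72 hours (Protocol 8.3.3 with the Table 15 footnote, 10.3.9.2, 10.3.10.1). Intensity is required too. A missing value should be rare, most of all among SAEs and pIMDs, and these appear in individual listings. A gap present at one data cut may be filled by a later analysis, and SAP Section 7.1 says major changes will be described in the study report. The study is descriptive, so no test depends on the rule. All of this stands, and it limits the likely size. It does not say what to do with the values that remain missing, which is the case 10.1.2.4 was written for.

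A second reply is that leaving grades unassigned is the SAP's convention. For solicited events, Section 10.1.2.3.1 lets missing daily recordings count in the any-grade row but not in specific grade rows. This stands against putting missing severity into the main Grade 3 tables, since that would report severe events that nobody recorded.

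Three stronger readings are tempting and are not supported:

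- **The events are recoded as unrelated or non-severe.** They are not. They carry the label UNKNOWN, remain in the any-unsolicited-AE tables, and are affected only in tables using the missing attribute. A participant with another known related or Grade 3 event in the same period still counts in the overall row. Exclusion from the numerators is itself inferred from the table definitions; the SAP could intend a separate UNKNOWN row.
- **Gaps cluster after the newest dose and so favour it.** Nothing in the documents shows this, and causality for SAEs and pIMDs is due at first report.
- **The related rate is understated by a substantial relative amount.** Any such percentage needs a missing share and a related share that the documents do not provide.

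**Conclusion.** The point holds as a small, one-directional gap in the current SAP. Under 10.1.2.4 read with 5.1.3 and 5.4.4, a participant whose only candidate event lacks a relationship or severity is in the denominator and not in the related or Grade 3 numerator. The rule can therefore understate those percentages and cannot overstate them.

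The size is unknown and probably small, given compulsory assessment. For 1 to 10 such participants (assumed), the most it can amount to is 0.1 to 1.0 percentage points at n = 990 and 0.3 to 3.0 at n = 330, reached only if every unassessed event truly qualifies. These are planned group sizes; with fewer vaccinated at a later dose, each participant weighs slightly more. The point rests on two readings: that UNKNOWN does not enter the related or Grade 3 numerators, and that the rule reaches SAEs and pIMDs. The second is supported by Section 10.1.2.4 including SAEs and by Protocol Section 10.3.1.1 recording every AE that is not solicited as unsolicited. It is a cheap improvement, not a flaw that threatens the trial's conclusions.

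**What to change.** Amend SAP Section 10.1.2.4 as follows:

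- In tables of causally related AEs, SAEs and pIMDs, a missing relationship counts as related, with a footnote giving the number so counted by group and dose.
- For missing severity, leave the main Grade 3 tables as they are, report the number of UNKNOWN severities by group and dose, and add one sensitivity table counting them as Grade 3.
- Keep UNKNOWN in the listings.

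For events both related and Grade 3, the relationship part follows the first rule and the severity part goes to the sensitivity table.

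The cost is a short SAP addition, a footnote and one extra table. Related percentages may become slightly less favourable, and may include an event that was not in fact related; the footnote lets the reader see how many. If no values are missing, no result changes.

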10.1.3. Data derivation

10.1.3.1. Age at first dose in years

When age at first dose is to be displayed in years, it will be calculated as the number of complete calendar years between the date of birth and the date of first dose. For example:

DOB = 10SEP1983, Date of first dose = 09SEP2018 -> Age = 34 years

DOB = 10SEP1983, Date of first dose = 10SEP2018 -> Age = 35 years

In this study, we will collect only the year of birth. The rules for handling missing day and/or month in the DOB are given in section 10.1.2.1.

212496 (RSV OA=ADJ-004) Statistical Analysis Plan

10.1.3.2. Temperature

Temperatures will be presented in degrees Celsius (°C). Temperatures reported in degrees Fahrenheit (°F) will be converted as follows:

Temperature (Celsius) = ((Temperature (Fahrenheit) - 32) x 5)/9

10.1.3.3. Numerical serology results

Numerical serology results will be derived from the content of IS.ISORRES in the SDTM dataset. For assays with a specific cut-off, the following derivation rules apply:

IS.ISORRES	Derived value
"NEG", "-", or "(-)"	cut-off/2
"POS", "+", or "(+)"	cut-off
"< value" and value is <= assay cut-off	cut-off/2
"< value" and value is > assay cut-off	Value
"> value" and value is < assay cut-off	cut-off/2
"> value" and value is >= assay cut-off	Value
"value" and value is < cut-off	cut-off/2
"value" and value is >= cut-off and value is <=ULOQ	value
"value" and value is > ULOQ	ULOQ*
All other cases	Missing

*This rule will be used to compute descriptive statistics (GMTs, fold increase,etc). All values might be displayed in scatter plots with individual results.

10.1.3.4. Geometric mean titres (GMTs) and concentrations (GMCs)

GMT or GMC calculations are performed by taking the inverse logarithm of the mean of the log titre or concentration transformations. Non quantifiable antibody titres or concentrations will be converted as described in section 10.1.3.3 for the purpose of GMT/GMC calculation. Cut-off values are defined by the laboratory before the analysis.

10.1.3.5. Onset day

The onset day for an event (e.g. AE, concomitant medication/vaccination) is the number of days between the last study dose and the start date of the event. This is 1 for an event occurring on the same day as a study dose (and reported as starting after study dose).

10.1.3.6. Duration of events

The duration of an event with a start and end date will be the difference between the start and end date plus one day, i.e. an event that starts on 3 March 2018 and ends on 12 March 2018 has a duration of 10 days.

The duration of solicited events will be calculated as the sum of the individual days with the adverse event reported at grade 1 or higher during the solicited event period.
CONFIDENTIAL

212496 (RSV OA=ADJ-004) Statistical Analysis Plan

10.1.3.7. Counting rules for combining solicited and unsolicited adverse events

For output combining solicited and unsolicited adverse events, all serious adverse events will be considered systemic events since the administration site flag is not included in the expedited adverse event CRF pages. Unsolicited adverse events with missing administration site flag will also be considered systemic.

Multiple events with the same preferred term which start on the same day are counted as only one occurrence.

10.1.3.8. Counting rules for occurrences of solicited events

When the occurrences of solicited events are summarized, each event recorded as having occurred during a specific period will be counted as only one occurrence regardless of the number of days on which it occurs. Also, in the case of co-administered study interventions, an administration site event recorded for a participant following multiple study interventions will be counted as only one occurrence.

10.1.4. Display of decimals

10.1.4.1. Percentages

Percentages and their corresponding confidence limits will be displayed with one decimal except for 100% in which case no decimal will be displayed.

10.1.4.2. Demographic/baseline characteristics statistics

The mean, median, and standard deviation for continuous baseline characteristics will be presented with one decimal.

The minimum and maximum values and quartile values (if required) will be presented with the same number of decimals as the observed values.

The maximum and minimum of transformed body temperatures will be displayed with one decimal.

10.1.4.3. Serological summary statistics

For each assay, geometric mean titers (GMT) or concentrations (GMC) and their confidence limits will be presented with one decimal, as well as GMT/GMC fold increase from pre-dose.

The mean, median, standard deviation and quartile values for frequency of RSVPreF3 specific-CD4+ and CD8+ T cells and for the fold increase (post over pre-vaccination) will be presented with one decimal. The minimum and maximum values will be presented with no decimal.

CONFIDENTIAL

212496 (RSV OA=ADJ-004) Statistical Analysis Plan

10.1.5. Statistical methodology

10.1.5.1. Exact confidence intervals around proportions

The exact confidence intervals around within-group proportions are derived using the method of Clopper and Pearson [Clopper, 1934].

